Patients with an ABCD-GENE<10 will be treated with clopidogrel (75 mg/qd). Patients with an ABCD-GENE≥10 score will be randomized in a 1:1 fashion to ticagrelor (60 mg/bid) or clopidogrel (75 mg/qd). Assigned treatment will be maintained for 30 +/- 5 days.

Blood will be collected at two visits by inserting a needle into a vein or from a catheter in a vein. The first visit will be after the PCI ideally before the subject has taken their antithrombotic medications (baseline); however, since patients may get discharged the same day of the PCI or may have already taken their daily dosing regimen, blood sampling will be allowed as this does not interfere with the study hypothesis. The second visit will be 30 +/- 5 days later. At this visit there will be two blood draws: the first before the subject has taken their antithrombotic medication (trough) and second 2 hours after the subject has taken their antithrombotic medication (peak).

PD measures will include a multitude of assays aimed to assess various measures of platelet reactivity, including purinergic and non-purinergic signaling pathways, and thrombin generation, as described below. Although the study will have an open-label design, laboratory personnel will be blinded to treatment assignments. Compliance with antithrombotic therapies will be assessed by interview and pill counting. During study treatment, major adverse cardiac events (death, myocardial infarction, stroke, and urgent revascularization procedures), serious adverse events (bleeding and other adverse events),

as well as non-serious adverse events will be collected. After completing the study, patients will resume an antithrombotic treatment regimen at the discretion of the treating physician.

Study population

A total of 84 CAD patients will be recruited In particular, 42 patients with an ABCD-GENE≥10 will be included and randomized to ticagrelor (n=20) or clopidogrel (n=20), while 42 patients will be in the ABCD-GENE<10 cohort. Patients will need to meet the following study entry criteria:

Inclusion criteria:

- Age \geq 18 years
- Willing and able to provide written informed consent
- Undergone successful PCI and treated with DAPT (aspirin plus a P2Y12 inhibitor) per standard of care
- On treatment with a novel oral anticoagulant (apixaban, dabigatran, edoxaban, or rivaroxaban) for any indication (dosing regimen will be according to standard of care and at the discretion of the treating physician)

Exclusion criteria:

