- 5) *T-TAS*: T-TAS is an automated microchip flow chamber system for the quantitative analysis of the thrombus formation process under blood flow conditions. T-TAS allows measurement of thrombus formation using the PL/AR-chips (Diapharma, West Chester Township, OH) [17-18]. The PL/AR-chips contains 25 capillary channels (width 40 μm, depth 40 μm) coated with type I collagen and is specifically designed for quantitative analysis of platelet thrombus formation, including platelet adhesion and aggregation, granule secretion, and thrombus growth in the absence of coagulation and fibrinolysis systems. In measurements using the PL/AR-chips, a blood sample collected in a hirudin and sodium citrate containing blood sampling tube. The platelet aggregates gradually increase in size and, in the process, occlude the capillary, resulting in an increase in flow pressure. In the present study, total platelet-derived thrombogenicity is expressed as the area under the flow pressure curve for the first 10 min for the PL/AR-

chips tested at a flow rate of 18 μ L/min (PL18-AUC10). Low PL18-AUC10 reflect reduced thrombus growth and rapid breakdown of the thrombus.

Study endpoints, sample size calculation and statistical analysis

The primary end point of our study will be levels of platelet reactivity, measured as PRU using the VN system, of ticagrelor versus clopidogrel at 30 days after randomization in patients with an ABCD-Gene score ≥ 10 . We hypothesize that ticagrelor 60 mg bid will lead to lower PRU compared with clopidogrel 75 mg qd. Based on previous studies [20], assuming a standard deviation of 55 and 80 PRU for ticagrelor and clopidogrel, respectively, a sample size of 17 patients per treatment group with valid primary end point data will be required to detect an absolute difference of 90 PRU between ticagrelor and clopidogrel with a 90% power and a 2-tailed alpha value of 0.05. Assuming a potential 25% in data attrition due to patient drop-out (e.g., due to side effects, unplanned use of parenteral antiplatelet therapies after randomization or withdrawal of consent) or invalid PD samples (e.g., due to hemolysis or technical reasons), a sample size of up to 21 patients per randomized group; 42 total will be randomized and an additional 42 in the control group. Thus, considering the 3 treatment arms, a total of up to 84 patients are expected to be enrolled to reach the sample size of patients with valid primary end point data required for the primary end point.

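### The sample-size figures do not follow from one another: the stated inputs need 14 per arm rather than 17, 21 per arm does not leave 17 after 25% loss, and the arms are given as both 20 and 21

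*Combined protocol and SAP*

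**What the plan says.** The calculation is in section 6 (Research Plan), under Study endpoints, sample size calculation and statistical analysis. The primary endpoint is platelet reactivity in patients with an ABCD-GENE score of 10 or more, "measured as PRU using the VN system, of ticagrelor versus clopidogrel at 30 days after randomization".

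- **Inputs:** "assuming a standard deviation of 55 and 80 PRU for ticagrelor and clopidogrel, respectively", chosen to "detect an absolute difference of 90 PRU between ticagrelor and clopidogrel with a 90% power and a 2-tailed alpha value of 0.05".
- **Evaluable number:** "a sample size of 17 patients per treatment group with valid primary end point data will be required".
- **Attrition:** "Assuming a potential 25% in data attrition due to patient drop-out" or unusable samples.
- **Number randomised:** "a sample size of up to 21 patients per randomized group; 42 total will be randomized", with another 42 in the lower-score cohort, making up to 84.

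The Study population part of section 6 also puts 42 patients in the higher-score cohort, but says they "will be included and randomized to ticagrelor (n=20) or clopidogrel (n=20" in each case, which totals 40.

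The primary analysis is ANCOVA with the baseline value as covariate. The sample-size paragraph names no test or formula and gives no correlation between baseline and 30-day values.

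**The concern.** This paragraph is the only justification of size for the only randomised comparison, and three of its links fail.

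1. The evaluable number is larger than the stated SDs, difference, power and alpha require.
2. The number randomised is too small to leave that evaluable number after the stated attrition.
3. The two sections disagree on the arm size.

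The first two errors pull in opposite directions, so what is at stake depends on which planning assumption was real. If the two stated SDs were meant, power is understated and the attrition slip does no harm. If 17 rests on a larger common SD, the attrition slip takes an unadjusted comparison below the 90% claimed. The text does not let a reader tell which.

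**Working it through.** **Inputs.** From the sample-size paragraph: SD 55 (ticagrelor) and 80 (clopidogrel), difference 90 PRU, power 90%, two-sided alpha 0.05, attrition 25%, 17 evaluable and up to 21 randomised per arm. From the Study design part: 1:1 allocation. From the Study population part: 42 randomised, shown as 20 and 20.

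**Step 1. Evaluable number on the stated inputs.**

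Normal formula: n = (1.960 + 1.282)² × (55² + 80²) / 90² = 10.507 × 9,425 / 8,100 = 12.23, so 13 per arm.

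The t-test with unequal variances (Welch degrees of freedom, noncentral t) gives:

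| Evaluable per arm | Power, SD 55/80 | Power, SD 80/80 |
|---|---|---|
| 13 | 89.0% | 78.6% |
| 14 | 91.3% | 81.7% |
| 15 | 93.2% | 84.5% |
| 16 | 94.6% | 86.8% |
| 17 | 95.8% | 88.9% |

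With the stated SDs, 14 is the smallest number that reaches 90%. The equal-variance t-test agrees (89.4% at 13, 91.6% at 14). At 17 per arm, power is 95.8%, and the difference detectable with 90% power is about 79 PRU rather than 90.

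**Step 2. Trying to reproduce 17.**

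With an SD of 80 in both arms, the normal formula gives 10.507 × (2 × 80²) / 90² = 10.507 × 12,800 / 8,100 = 16.60, so 17. This matches, but it discards the stated ticagrelor SD of 55, and the t-based power at 17 is then 88.9%, just under 90%. One-sided testing, other power levels (80%, 85%, 95%) and a simple average of the SDs do not give 17 with the remaining stated inputs.

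**Step 3. Attrition.**

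- To keep 17 after 25% loss: 17 / 0.75 = 22.7, so 23 per arm (46 in total).
- The plan's 21 matches 17 × 1.25 = 21.25, rounded down. That adds a quarter of the evaluable number, whereas the loss is a quarter of those randomised.
- From 21 randomised: 21 × 0.75 = 15.75 remain. From 20 randomised: 20 × 0.75 = 15 remain.
- Keeping 17 of 21 tolerates a loss of 4/21 = 19.0%. Keeping 17 of 20 tolerates 3/20 = 15.0%.
- If each patient is lost independently with probability 0.25, the chance that an arm of 21 keeps at least 17 is 0.367. For both arms it is 0.367² = 0.135.

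**Step 4. Arm sizes.**

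20 + 20 = 40, against 42 in the same sentence and 21 per arm (42 in total) in the sample-size paragraph.

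**The case against.** The strongest reply is that the error is on the safe side. On the stated SDs, even 20 per arm with the full 25% loss leaves 15 and 93.2% power. Against the 14 actually needed, the chance that both arms of 21 keep enough is about 76% (0.870²), so the 13.5% figure looks bad only because it is measured against the plan's own 17. This stands: the trial is not underpowered on the inputs it states.

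Second, the origin of 17 is a guess. An SD of 80 in both arms is the plainest route, but not the only conceivable one. A Bonferroni division of alpha by three gives 89.5% power at 17, and a worst-case efficiency allowance for a rank test gives 14 / 0.864 = 16.2, which also rounds up to 17. The plan states none of these, and none agrees with the inputs as written. So the power figures for SD 80 in both arms are a sensitivity case and do not show a shortfall.

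Third, the analysis is ANCOVA, and adjusting for baseline would, if anything, lower the number needed. Even with SD 80 in both arms, an assumed baseline correlation of 0.2 restores 90.1% at 17, and 0.4 restores 90.0% at 15. The plan gives no correlation, so this softens the sensitivity case without settling it, and on the stated SDs it moves the requirement further from 17.

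Fourth, 20 versus 21 is probably a slip, because every total (42 and 84) supports 21. That is likely right, but it still needs correcting. Calling 21 an upper limit does not help the attrition step, since a ceiling below 23 cannot deliver 17 at the stated loss.

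**Conclusion.** The concern holds. On the stated inputs the requirement is 14 evaluable patients per arm (13 by the normal formula), not 17, and 17 gives about 96% power, not 90%. The 21 randomised leave about 16 per arm after 25% loss, not 17. The Study population section accounts for 40 of the 42 patients.

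The consequence depends on the SDs. With 55 and 80, power after attrition is about 93% to 95% and the design is adequate. With 80 in both arms, an unadjusted comparison has about 84% to 87% at 15 to 16 per arm, below the 90% claimed. These figures assume normally distributed PRU, equal arms and an unadjusted two-sample t-test. This is a defect in the justification as written and should be corrected; it does not show that the trial is too small.

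**What to change.** Rewrite the sample-size paragraph around the planned enrolment:

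- Name the test and the SDs actually used. If they are 55 and 80, the text could read: with SDs of 55 and 80 PRU, 14 evaluable patients per arm give 91% power to detect 90 PRU at two-sided alpha 0.05; 21 per arm (42 in total) will be randomised; after 25% loss about 15 per arm remain, giving about 93% power.
- If an SD of 80 in both arms was intended, say so and restate the power at 15 to 16 evaluable per arm as about 84% to 87% for an unadjusted comparison. Any credit taken for baseline adjustment should come with the assumed correlation and its source.
- Remove the statement that 17 evaluable patients per arm are required, or show the method that leads to it.
- In the Study population section, change the arm sizes to 21 and 21 so that they add to 42.

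This costs wording only. Enrolment, treatment and the analysis do not change.

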Additional exploratory end points will include the comparisons between clopidogrel-treated patients with ABCD-Gene score<10 and the other 2 arms, as well as comparisons between groups of rates of HPR. For baseline characteristics, categorical variables will be expressed as frequencies and percentages; continuous variables will be

presented as mean ± SD or median [IQR]. Continuous variables will be analyzed for normal distribution with the Kolmogorov-Smirnov test. Comparisons for the primary end point as well as for other intergroup comparisons of continuous variables will be performed with an analysis of covariance with a general linear model with baseline value of the corresponding platelet function test as a covariate. Intragroup comparisons will be performed using a mixed linear model. Comparisons for categorical variables, including rates of HPR will be performed with the Chi square test or Fisher exact test. A p-value < 0.05 will be considered statistically significant. Statistical analysis will be performed with SPSS version 25 software (SPSS Inc.). Data analysis will be performed at the University of Florida. Data transfer will occur in a HIPAA de-identified manner. Data from The Netherlands will arrive coded so that source of data can be easily known."

The PD population will include all patients with PD data and without a major protocol deviation thought to affect significantly the PD of ticagrelor or clopidogrel. The PD population will be used for analysis of all primary and secondary PD variables. Erroneously treated patients (eg, those randomized to one treatment but actually given the other) will be accounted for based on the actual treatment received.

All patients who received at least 1 dose of study drug will be included in the safety population. Safety will be evaluated by assessment of adverse events (including bleeding and ischemic). Adverse events will be collected up to completion of the study. Bleeding events will be classified according to BARC (Bleeding Academic Research Consortium) criteria [27]. Stent thrombosis will be classified according to ARC (Academic Research Consortium) definitions [28]. MI, including peri-procedural MI, will be defined according to the universal definition [29]. Ischemic stroke will be defined as

an ischemic cerebral infarction caused by an embolic or thrombotic occlusion of a major intracranial artery. Death will be considered cardiac in origin unless obvious non-cardiac causes can be identified.

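### The equal-variance ANCOVA does not fit the plan's own SDs of 55 and 80 PRU for exploratory comparisons with the larger score <10 cohort, and the plan does not say which groups enter each model

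*Combined protocol and SAP*

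**What the plan says.** All of this stands in section 6 (Research Plan), under the heading on endpoints, sample size and statistical analysis.

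- **Planning values.** The sample size is derived "assuming a standard deviation of 55 and 80 PRU for ticagrelor and clopidogrel, respectively". It then states that "a sample size of 17 patients per treatment group with valid primary end point data will be required". The aim is "to detect an absolute difference of 90 PRU between ticagrelor and clopidogrel", and the calculation is made "with a 90% power and a 2-tailed alpha value of 0.05".
- **Group sizes.** After an allowance for attrition the plan gives "a sample size of up to 21 patients per randomized group", and then "42 total will be randomized and an additional 42 in the control group". The groups are therefore 21, 21 and 42.
- **Analysis.** The method for the primary comparison, "as well as for other intergroup comparisons of continuous variables will be performed with an analysis of covariance with a general linear model", takes the baseline value of the same platelet function test as covariate.
- **Contrasts.** The primary one is ticagrelor versus clopidogrel within score ≥10. Comparisons of the score <10 cohort with each of the other two arms are listed separately, as exploratory.

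The only distributional check named is a Kolmogorov-Smirnov test for normality. The section does not mention unequal variances or robust standard errors. It does not say whether each comparison has its own model or all three groups share one. It gives no SD for the score <10 cohort and no residual SD after baseline adjustment.

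**The concern.** An ordinary general linear model uses one residual variance for every group. The plan's own SDs imply a variance ratio of (80/55)² = 2.1, and the score <10 cohort is twice the size of each randomised arm. Unequal variances combined with unequal group sizes are the conditions in which a pooled standard error goes wrong. It becomes too wide when the smaller group has the smaller variance, and too narrow when the smaller group has the larger variance.

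Two things are at stake. The exploratory comparisons with the score <10 cohort may carry wrong confidence intervals and p-values, all read against the same 0.05 threshold. And because the plan does not say which groups enter each model, a non-randomised cohort could influence the standard error of the randomised primary comparison.

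**Working it through.** **Inputs from the plan.** SDs 55 and 80, difference 90 PRU, 90% power, two-sided alpha 0.05, 17 evaluable per randomised arm, groups 21/21/42. **Assumed:** SD 80 in the score <10 cohort (varied below), and the SD ratio surviving baseline adjustment.

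**1. The plan's own figure.** n per arm = (1.960 + 1.282)² × (s₁² + s₂²)/90².

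- SDs 55 and 80: 10.507 × (3,025 + 6,400)/8,100 = 12.2, so 13 per arm (14 with the t distribution).
- SD 80 in both arms: 10.507 × 12,800/8,100 = 16.6, so 17.

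The stated 17 therefore matches a common SD of 80 and is conservative for the stated SDs. At 17 per arm, power under 55 and 80 is about 96%.

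**2. Standard errors at 21/21/42, score <10 SD 80.** True SE = √(s₁²/n₁ + s₂²/n₂). Model SE = pooled SD × √(1/n₁ + 1/n₂).

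- Three-group pooled variance: (20×3,025 + 20×6,400 + 41×6,400)/81 = 5,567, SD 74.6.
- Two-group pooled variance, ticagrelor and score <10: (20×3,025 + 41×6,400)/61 = 5,293, SD 72.8.

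| Contrast | True SE | Two-group model (ratio) | Three-group model (ratio) |
|---|---|---|---|
| Ticagrelor vs clopidogrel, score ≥10 (primary) | 21.19 | 21.19 (1.00) | 23.03 (1.09) |
| Ticagrelor vs score <10 | 17.22 | 19.44 (1.13) | 19.94 (1.16) |
| Clopidogrel ≥10 vs <10 | 21.38 | 21.38 (1.00) | 19.94 (0.93) |

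The ratios are practically the same at 17/17/34, which applies the 17/21 evaluable share to all groups. The study population paragraph gives 20 per randomised arm; at 20/20/42 the three-group ratios are 1.09, 1.17 and 0.93.

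**3. Type I error.** ANCOVA was simulated with 15,000 null trials per setting, at 17/17/34 and 21/21/42, with baseline correlation 0 and 0.5 (nominal 5%):

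| Contrast | Two-group | Three-group |
|---|---|---|
| Primary | 4.8 to 5.2% | 3.3 to 3.7% |
| Ticagrelor vs score <10 | 2.8 to 3.0% | 2.5 to 2.6% |
| Clopidogrel ≥10 vs <10 | 5.0 to 5.2% | 6.6 to 7.1% |

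With HC3 standard errors, the two-group ticagrelor versus score <10 error is about 4.4%. Primary power at 17/17/34 without baseline correlation is 94.7% in a three-group fit and 95.4% in a two-arm fit.

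**4. Range over the missing SD** (model SE / true SE at 21/21/42):

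| Score <10 SD | Ticagrelor vs <10, two-group | Ticagrelor vs <10, three-group | Clopidogrel ≥10 vs <10, two-group | Clopidogrel ≥10 vs <10, three-group | Primary, three-group |
|---|---|---|---|---|---|
| 55 | 1.000 | 1.129 | 0.885 | 0.855 | 0.905 |
| 70 | 1.084 | 1.148 | 0.956 | 0.903 | 1.010 |
| 80 | 1.129 | 1.158 | 1.000 | 0.933 | 1.087 |
| 100 | 1.201 | 1.175 | 1.077 | 0.986 | 1.252 |

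In a three-group fit the primary ratio equals 1 when the cohort's SD is √((55² + 80²)/2) = 68.6. Below that the primary standard error is too narrow, and above it too wide. In a two-arm fit with equal numbers the ratio is 1 whatever the cohort's SD.

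**The case against.** The strongest reply is that the plan names a method and does not describe a joint model. The primary is confined to score ≥10 patients and the cohort comparisons are listed apart, so separate two-group fits are at least as natural a reading. Under that reading the primary is correct with equal arms, the clopidogrel contrast is correct if both SDs are 80, and only one exploratory comparison is off, in the conservative direction. This stands. What remains is that the comparison is still about 13% off at SD 80, and that the text leaves the choice of model open.

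A reader might infer that the primary interval is needlessly wide. The documents do not support that: it requires a three-group fit, which is not stated, and a cohort SD above 68.6, which is not given.

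A reader might also infer that unequal drop-out will inflate the primary error rate. The plan's wording is "Assuming a potential 25% in data attrition due to patient drop-out" or invalid samples, one figure with no difference by arm. The only arm-specific hint is in section 7: discontinuation for dyspnea on ticagrelor, with a switch to clopidogrel. That points to fewer ticagrelor patients, which makes the pooled test conservative. At 14 ticagrelor versus 21 clopidogrel the standard error is 7.7% too wide (type I error about 0.038). The inflated case, 21 versus 14 (7% too narrow, about 0.07), needs no ticagrelor loss and a one-third clopidogrel loss, which nothing in the documents suggests.

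It is also fair to say that HC3 gains nothing for a balanced two-arm primary: simulated type I error moves from 0.050 to 0.040.

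**Conclusion.** The point holds, and it is minor. Under the plan's SDs, and with SD 80 assumed in the score <10 cohort, the ticagrelor versus score <10 standard error is 13% too wide in a two-group fit and 16% in a three-group fit, with type I error about 0.025 to 0.03. Over cohort SDs of 55 to 100 the ratio runs from 1.00 to 1.20 (two-group) and from 1.13 to 1.18 (three-group).

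The other effects at SD 80 arise only if all three groups share a model. The clopidogrel ≥10 versus <10 standard error is then about 7% too narrow (type I error about 0.065 to 0.07), and the primary standard error depends on the non-randomised cohort. A balanced two-arm primary fit is unaffected, and primary power stays above 90% at SD 80 under either fit. The primary conclusion is not threatened.

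The sizes depend on two things the documents do not give: the cohort's SD, and whether the 55 to 80 ratio persists after baseline adjustment.

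**What to change.** In the statistical analysis text of section 6:

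1. State that the primary ANCOVA is fitted to the two randomised arms only.
2. For contrasts with the score <10 cohort, specify a separate residual variance per group or HC3 standard errors.
3. State in advance that the same option applies to the primary if the analysed arm sizes turn out unequal.

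The cost is a sentence or two and a different analysis option. No extra patients or data are needed. A mixed linear model, already named for the intragroup comparisons, can carry a separate residual variance per group. The downside is a slight loss of efficiency if the variances prove equal.

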Results from blood tests performed within the last 30 days will be considered valid for screening. Patients will undergo genetic testing to identify CYP2C19 genetic status using the Spartan assay or central lab. Randomization will occur once genetic testing results become available, ideally prior to hospital discharge. However, for patients discharged

[figure not shown]
before having results available or over the weekend they will be allowed to return for their randomization within 3 days from test results. Patients with an ABCD-GENE≥10 score will be randomized in a 1:1 fashion to ticagrelor (60 mg/bid) or clopidogrel (75 mg/qd). Patients with an ABCD-GENE<10 will be treated with clopidogrel (75 mg/qd).

Since the choice of P2Y₁₂ inhibitor during the PCI procedure may vary (commercially available agents include clopidogrel, ticagrelor and prasugrel), the following recommendations will be made based on the agent chosen and the treatment assignment: a) patients assigned to clopidogrel and also treated with clopidogrel during PCI will continue with a 75 mg/qd maintenance dose for the duration of the study; b) patients assigned to clopidogrel but treated with ticagrelor or prasugrel during PCI will receive a 600 mg loading dose clopidogrel followed by a 75 mg/qd maintenance dose for the duration of the study; c) patients assigned to ticagrelor and also treated with ticagrelor during PCI will continue with ticagrelor 60 mg bid maintenance dose for the duration of the study; d) patients assigned to ticagrelor but treated with clopidogrel or prasugrel during PCI will be administered a 180 mg loading dose followed by a 60 mg bid for the duration of the study. Administration of randomized treatment will occur prior to hospital discharge as would occur per standard of care for administration of the next dose of P2Y₁₂ inhibiting therapy. The use of a loading dose when switching agent is in line with consensus recommendations for switching P2Y₁₂ inhibiting therapy [19]. The clopidogrel 600mg loading dose and 75 mg/qd maintenance dose regimen is in line with practice recommendations [1]. The ticagrelor 180 mg loading dose regimen is in line with practice guidelines; the 60 mg bid maintenance dose regimen was chosen in light of recent data that this dose provides platelet inhibitory effects not dissimilar from the 90 mg bid dosing

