regimen but with less side effects and more efficacious platelet inhibitory effects than clopidogrel, including after PCI [1,20]. All patients will maintain aspirin 81 mg/qd at least for the duration of hospital stay. Aspirin therapy will be discontinued at time of hospital discharge or at 7 days after PCI at the discretion of the treating physician in patients deemed to be at high ischemic risk, as per standard of care for patients requiring concomitant treatment with a P2Y₁₂ inhibitor and an OAC [14,15].

Assigned treatment will be maintained for 30±5 days. PD assessments will be conducted at 3 time points: i) baseline (while on standard of care DAPT therapy): day after PCI, ideally before the administration of the morning dose of P2Y₁₂ inhibiting therapy and OAC (trough levels of platelet reactivity); however, since patients may get discharged the same day of the PCI or may have already taken their daily dosing regimen, blood sampling will be allowed as this does not interfere with the study hypothesis; patients will continue to take their morning dose of aspirin and all other standard of care therapies; ii) 30±5 days after randomization: before (trough levels of platelet reactivity) and 2 hours after (trough levels of platelet reactivity) the administration of the morning doses of P2Y₁₂ inhibiting therapy and OAC (trough levels of platelet reactivity); patients will take all other standard of care therapies. Figure 2 illustrates the overall study design and a further breakdown of what will occur during the course of the study:

- Patients will first be screened by research personnel to see if they are eligible for the study. Results from blood tests performed within the last 30 days which patients would have performed because of their stent procedure will be considered valid for screening purposes.
- If it is a woman of childbearing potential, a pregnancy test will be done. If the subject is found to be pregnant, their participation in this study will end.
- If they are eligible for the study based on the screening results, they will start the study procedures as outlined below:
 - Genetic test buccal swab. This swab is being done to determine CYP2C19 genetic status.
 - The physician will determine the ABCD-GENE score as described in Figure
 1. This score is calculated by looking at the subject's CYP2C19 genetic

status and clinical information, including age, BMI, renal function, and diabetic status.

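### The primary ANCOVA adjusts for a baseline PRU measured on different P2Y12 inhibitors and has no term for that agent: valid overall, but cheaply improved

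*Combined protocol and SAP*

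**What the plan says.** The protocol (section 6, Study design) expects the P2Y12 inhibitor used at PCI to vary: "commercially available agents include clopidogrel, ticagrelor and prasugrel". Its rules a) to d) depend on that agent. Rules b) and d) cover patients whose PCI agent differs from the assigned one. Allocation in the cohort with a score of 10 or more is plain 1:1, and no stratification by agent is described.

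The first PD sample is defined as "baseline (while on standard of care DAPT therapy): day after PCI". It is therefore taken on the PCI-time agent.

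The statistical section specifies the primary comparison, and the other between-group comparisons of continuous variables, as an "analysis of covariance with a general linear model with baseline value of the corresponding platelet function test as a covariate". It gives no agent term and no sensitivity analysis on this point. The remark in Study design that sampling will not interfere with the hypothesis concerns whether the dose had already been taken, not which drug it was.

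**The concern.** A low baseline PRU can mean low underlying reactivity, which may predict day-30 PRU. It can also mean only that the patient received ticagrelor or prasugrel at PCI. After about 30 days on assigned treatment, the second meaning should predict little or nothing. One pooled slope treats both alike. If one arm happens to hold more patients on a potent agent at PCI, the model corrects the treatment difference for a baseline gap that has no bearing on the day-30 value.

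What is at stake is the size of the reported PD difference in a trial with 17 evaluable patients per arm, and some of the precision that baseline adjustment is meant to give. The same model serves the other P2Y12-dependent assays, so the question recurs there.

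**Working it through.** **1. The plan's own figure.** Inputs from the statistical section: "assuming a standard deviation of 55 and 80 PRU for ticagrelor and clopidogrel, respectively", and an "absolute difference of 90 PRU between ticagrelor and clopidogrel with a 90% power and a 2-tailed alpha value of 0.05".

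- With SD 80 in both arms: n = 2 × (1.960 + 1.282)² × 80² / 90² = 2 × 10.51 × 6400 / 8100 = 16.6, so 17. This reproduces "a sample size of 17 patients per treatment group with valid primary end point data will be required".
- With the two SDs as written: 10.51 × (55² + 80²) / 90² = 10.51 × 9425 / 8100 = 12.2, so 13 (14 by the exact t-test). The stated 17 is on the safe side.
- Standard error of the unadjusted difference at 17 per arm: √(9425 / 17) = 23.5 PRU.

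**2. Mechanism.** The adjusted difference is (ȳ_T − ȳ_C) − b(x̄_T − x̄_C), where x is baseline PRU and b the pooled slope. Let g be the baseline gap between clopidogrel and the potent agents. If the ticagrelor arm has k more potent-agent patients than the clopidogrel arm, x̄_T − x̄_C is on average −g·k/17. If the PCI-time agent has no effect left at day 30, ȳ_T − ȳ_C is unaffected, so the estimate moves by

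shift = b × g × k/17.

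This is towards zero when the excess is in the ticagrelor arm and away from zero when it is in the clopidogrel arm. Illustration with an assumed slope of 0.3 and gap of 120: 0.3 × 120 × 3/17 = 6.4 PRU.

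**3. Slope.** With share p on a potent agent, within-agent baseline SD s and correlation ρ between underlying reactivity and day-30 PRU, approximately

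b = ρ × 67.5 × mean(s) / [mean(s²) + p(1 − p)g²],

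where 67.5 = (80 + 55)/2. The following are assumptions, not figures from the documents: p, g, ρ, and s = 60 on clopidogrel and 45 on a potent agent.

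- Low end (p = 0.5, g = 150, ρ = 0.3): b = 0.3 × 67.5 × 52.5 / (2812.5 + 5625) = 0.126. Shift for k = 3 is 0.126 × 150 × 3/17 = 3.3; for k = 5 it is 5.6.
- High end (p = 0.2, g = 150, ρ = 0.6): b = 0.6 × 67.5 × 57 / (3285 + 3600) = 0.335. Shift for k = 3 is 8.9; for k = 5 it is 14.8.
- If ρ = 0, then b is zero on average and there is no shift.

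Simulated trials (17 per arm, SDs 55/80, true difference 90, p 20–50%, g 100–150, ρ 0.3–0.6) agree: about 3–9 PRU for an excess of 3 and 5–15 PRU for an excess of 5. An agent term cuts the average shift per patient of imbalance from 1.1–2.8 PRU to within ±0.3 PRU. At a share of 10%, the shift can be larger once an imbalance exists (up to about 18 PRU for an excess of 5 or more), but such an imbalance is then very rare.

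**4. How often.** Difference between two binomial counts of 17, either direction:

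| Share on a potent agent | Imbalance ≥3 | Imbalance ≥5 |
|---|---|---|
| 10% | 15% | 1% |
| 20% | 28% | 5% |
| 30% | 35% | 9% |
| 50% | 39% | 12% |

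Each direction has half of these chances.

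**5. Behaviour over all randomisations** (same simulations, p 20–50%).

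| | Planned ANCOVA | With agent term |
|---|---|---|
| Mean error (PRU) | within ±0.5 | within ±0.7 |
| SD of the estimate | 20.9–23.8 | 19.6–23.6 |
| Power at 90 PRU | 0.955–0.986 | 0.958–0.994 |

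Type I error of the planned model was 0.046–0.063 in runs of 3,000. In the run that gave 0.063, the unadjusted test gave 0.065.

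**6. Precision.** With half on potent agents, g = 150 and ρ = 0.5 throughout, the SD is 23.8 unadjusted, 22.9 planned and 21.6 with the agent term, a gain of 1.3/22.9 = 6%. The most favourable case simulated (ρ = 0.6 in both arms, same p and g) goes from 22.3 to 19.6, or 12%. If correlation exists only in patients on clopidogrel at both times, there is no gain (23.9 versus 24.1). If baseline predicts nothing, the term costs 24.0 to 24.5, or 2%.

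**The case against.** ANCOVA on the baseline value is a standard, valid, prespecified analysis. Any small trial has chance imbalance in something that is not modelled, and a shift that exists only given such an imbalance is not bias. The documents give no agent mix, and section 4 (Background) calls clopidogrel the agent of choice in this population, which argues against a half-and-half baseline. With 10% on potent agents, about 3 of 34 patients would inform the agent effect. The proposed model also still uses one slope. In simulated trials, the models with and without the term disagreed on significance in only 1–2% of cases.

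Most of this stands, and it is why the point ranks low. Two parts do not dispose of it. A lower share makes imbalance rarer but does not shrink the shift once it occurs. And the unadjusted comparison is not displaced by the agent mix, so here the adjustment itself introduces the error, through a variable that the protocol foresees and has to know for every patient.

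A reader might also infer that the planned model throws away most of the precision that baseline PRU could give. That is not supported in general. It holds in the first case of step 6, where the planned model secures 0.9 of a possible 2.2 PRU reduction in SD. At a 20% share with ρ = 0.5 and the same gap, the SDs are 23.8, 22.2 and 21.3, so the planned model already secures 1.6 of 2.5. Where correlation is confined to patients on clopidogrel at both times, there is almost nothing to lose.

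**Conclusion.** The concern holds as a conditional one. Given a chance imbalance in PCI-time agent, the planned model moves the primary estimate by about 3–9 PRU (excess of 3) or 5–15 PRU (excess of 5), at shares of 20–50%. That is at most about 15/90 = 17% of the target difference and is below one standard error. The figures rest on an assumed agent share, baseline gap and correlation, and on the PCI-time agent having no effect left at day 30. None of these is in the documents, and the shift vanishes if baseline PRU does not predict day-30 PRU.

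It would be wrong to read this as a biased primary analysis or an inflated error rate. Randomisation keeps the planned estimate centred and the test close to nominal. Nor would it plausibly reverse the primary conclusion, since power at 90 PRU exceeds 95% under either model. The sample size need not change.

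**What to change.** In the statistical section, specify the primary ANCOVA with treatment, baseline PRU and PCI-time P2Y12 agent (clopidogrel versus ticagrelor or prasugrel), and tabulate that agent by arm. The same sentence can cover the other P2Y12-dependent assays.

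The agent is already needed to apply rules a) to d), so no new data are required. The cost is one sentence, one degree of freedom and an SD about 2% larger if baseline has no predictive value. The term should be fixed before the data are seen, because adding it after noticing an imbalance would be a post hoc choice. If the sponsor prefers to keep the planned model as primary, a prespecified sensitivity analysis with the agent term would show whether the estimate depends on it. Priority is low.
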